### 4.2. Recruitment

The following information was included in the CONSORT flow diagram. All counts will be reported as total and by IRC.

- Reasons for exclusion when assessed for eligibility
  - Not pregnant/no viable fetus
  - Mother outside of age range
  - Does not/will not primarily cook with biomass
  - Planned to move/moved away
  - Unwilling to participate
  - Gestational age out of range
  - Not a singleton
  - Smoker
  - Not in study area
  - Withdrawn by study team/not pursued further
- Participants determined to be ineligible after randomization
- Reasons for exits after randomization
  - Voluntary withdrawal prior to birth and after birth
  - Withdrawn by study team prior to birth and after birth
  - Moved away prior to birth and after birth
  - Pregnancy loss (termination/miscarriage/stillbirth)

### 4.3. Withdrawal/follow-up

The study recorded reasons for exit classified into several categories:

- Not eligible
- Participant voluntary withdrawal
- Withdrawn by study team
- Moved away from study area (periods of intermittent moves outside study area will be excluded)
- Deceased
- Lost to follow up
- Mother abortion/miscarriage/stillbirth
- Child death
- Other

For exits due to eligibility, voluntary withdrawal and withdrawal by study team, several pre-specified reasons were used, as well as the option to fill in other reasons. The last completed visit was also recorded. Reasons for withdrawal and loss to follow-up were ascertained as soon as possible.

If reason for study exit is voluntary withdrawal

- Procedures too intrusive
- Procedures too time-consuming
- Do not see value in the study
- Family does not want me to participate
- Do not want to be in assigned group
- Other

If reason for study exit is withdrawn by study team:

- Repeated resistance to study procedures
- Danger to study personnel
- Other

## 5. KEY VARIABLE DEFINITIONS AND DATA COLLECTION

In this section, we describe the data used for the exposure-response analysis of HAP exposure and severe infant pneumonia, as defined by HAPIN and WHO.

### 5.1 Overview of Key Analysis Variables for Manuscript

Personal HAP exposures were measured directly in pregnant women/mothers both prenatally and postnatally, including fine particulate matter (PM2.5), black carbon (BC), and carbon monoxide (CO). Postnatally, we measured area concentrations in the kitchen and infant's bedroom. Personal exposures to PM2.5 and CO in infants will be assessed indirectly. Specifically, we will use logging transponders on the mother and in the kitchen and bedroom, and the infant will wear emitters. We have developed and validated an interpolation algorithm to estimate indirect exposures in infants; however, we will consider different approaches to estimate personal exposure in infants if missingness of emitter/transponder logging data is ≥10%. We summarize HAP exposures in the trial in Table 1. Per protocol, exposure variables used in exposure-response models were calculated as weighted averages of subsets of these assessments (Section 6.1). However, we also explore performance of alternative predictions of longer-term exposure using our exposure validation sub-study.

**Table 1. HAP exposures measured in the trial**

Measurement time	Notation	Personal exposure in pregnant woman	Personal exposure in mother	Area concentration in kitchen	Area concentration in bedroom	Indirect measurement in children
9 – 19 weeks' gestation	BL	PM 2.5 , BC, CO				
24 – 28 weeks' gestation	P1	PM 2.5 , BC, CO				

32 – 36 weeks' gestation	P2	PM 2.5 , BC, CO				
Child is 3 months of age	B1		PM 2.5 , BC, CO	PM 2.5 , BC, CO	PM 2.5 , BC, CO	PM 2.5 , CO
Child is 6 months of age	B2		PM 2.5 , BC, CO	PM 2.5 , BC, CO	PM 2.5 , BC, CO	PM 2.5 , CO
Child is 12 months of age	B4		PM 2.5 , BC, CO	PM 2.5 , BC, CO	PM 2.5 , BC, CO	PM 2.5 , CO

The main outcome for this analysis is the same as in the intention-to-treat analysis (infant severe pneumonia). We will also analyze a set of predefined alternative definitions of pneumonia that cover a range of sensitivity, specificity, and disease severity. There were 175 HAPIN severe pneumonia during the follow-up period, among 2984 infants (6%), and there were 267 severe WHO pneumonias (9%). These respiratory endpoints are summarized in Table 2:

Table 2. Pneumonia and other respiratory outcomes	
Parameter	Definition
(HAPIN) severe infant pneumonia	
 
Presence of cough and/or difficult breathing and at least one general danger sign and primary endpoint pneumonia on a lung ultrasound or chest x-ray
 
Presence of cough and/or difficult breathing and hypoxemia (measured via pulse oximetry, SpO2)
 
Children who died but their death is attributed to pneumonia by verbal autopsy
 
 
General danger signs for all participants include any of the 5 signs of:
 
 
Unable to drink or breastfeed
 
Vomiting everything
 
Convulsions
 
Lethargy or unconscious
 
Stridor at rest
 
Severe acute malnutrition (weight-for-length z-score < -3 or weight-for-age < -3 if length is missing)
 
 
There are 4 additional general danger signs for participants <2 months of age (neonatal danger signs):
 
 
Unable to feed
 
Grunting
 
Not moving at all or moves with stimulation only
 
Severe chest indrawing
 

IMCI WHO severe infant pneumonia	
Cough and/or difficult breathing and
 
 
any general danger sign (unable to drink or breastfeed, vomiting everything, convulsions, lethargic or unconscious) or
 
stridor at rest or
 
severe acute malnutrition or
 
HIV infection or exposure (if chest indrawing also) or
 
Hypoxemia (SpO2 <90%)
 

## 5.2. Identification of Confounders

To assess conditions for identifiability of causal effects of HAP exposure on pneumonia, we gathered expert views on the causal relations among variables related to exposure, pneumonia, or the HAPIN study design. Confounder selection was based on conceptual directed acyclic graphs as shown in Appendix figures and code.

A key feature of this exposure-response analysis for causal inference is that it is conducted within the population of a randomized intervention trial that created a strong exposure contrast by arm. Nevertheless, HAP exposure is determined by many other factors and it is likely that some of these factors are common

causes of severe infant pneumonia or share a common cause with severe infant pneumonia. Since exposures are qualitatively and quantitatively different during gestational and postnatal periods, we have included a time-varying exposure that can take one value during pregnancy (HAP1\_T) and another after birth (HAP2\_T). The DAG can be analyzed for adjustment sets for estimating effects of prenatal exposure, postnatal exposure, or both of these exposures.

A general assumption in the DAG in appendix Figure 1 is that the HAPIN trial intervention can have direct effects on respiratory disease or effects that are not pathways going through HAP exposure. In particular, the provision of free fuel can have a large impact on the household economy and influence behaviors. For example, we have assumed the intervention has direct effects on breastfeeding, nutrition, healthcare seeking, maternal vaccination, and pneumonia. However, there was not a consensus in the research group about the pathway between intervention and severe pneumonia and the downside to conditioning on intervention could be reducing study power by reducing residual exposure variability (i.e.. greater variance of exposure-response estimates). The primary analysis will not condition on intervention or types of fuels and stoves.

We also considered measurement error as a source of bias. The DAG includes nodes for measured (e.g. exposures HAP1\_M and HAP2\_M, and outcomes Pneumonia\_M) and true values of HAP exposure and severe pneumonia. These allow representation of structures that can be important for understanding information bias. For example, the HAPIN intervention can influence the probability that a caregiver with a sick child seeks care at a surveillance site or that the healthcare seeking event results in screening by HAPIN staff. Moreover, the spatiotemporal and dispersion properties of HAP would suggest that error in indirect exposure assessment is likely to be dependent on intervention arm and other determinants of exposure.

Based on our DAG, we have identified the following variables, for which we have data, as the minimal adjustment set to identify the effect of prenatal HAP exposure on severe infant pneumonia: crowding (number sleeping in house), intervention IRC, nutrition history of breastfeeding, SES, sex, birthweight, and a data for small for gestational age (z-score). As noted, intervention status will not be included for either pre or post-natal exposure as it will be superceded by measured exposure level.

Birthweight would need to be included to reduce bias for estimating effects of postnatal exposure, but conditioning on birth weight could bias estimates of prenatal exposure because it is suspected of being on the causal pathway, so caution must be exercised here.

We will conduct sensitivity analyses to assess variability between estimates with alternative sets of appropriate covariates. Confounders selected from adjustment sets are found in the HAPIN codebook.

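### Section 5.2 omits trial arm from an adjustment set said to follow from the DAG, yet assumes arm effects that leave back-door paths open, and no arm-adjusted analysis is named

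*SAP*

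**What the plan says.** All the key statements are in SAP section 5.2.

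- **Arm drives exposure.** The analysis sits inside a "randomized intervention trial that created a strong exposure contrast by arm".
- **Arm may act outside smoke.** As a general DAG assumption, "the HAPIN trial intervention can have direct effects on respiratory disease or effects that are not pathways going through HAP exposure". More specifically, "we have assumed the intervention has direct effects on breastfeeding, nutrition, healthcare seeking, maternal vaccination, and pneumonia".
- **Arm may change detection.** "the HAPIN intervention can influence the probability that a caregiver with a sick child seeks care at a surveillance site", and also whether the visit leads to a study screening.
- **Arm may change exposure error.** "error in indirect exposure assessment is likely to be dependent on intervention arm and other determinants of exposure".
- **Arm is left out.** "The primary analysis will not condition on intervention or types of fuels and stoves".

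Section 5.2 gives three reasons for leaving arm out. The research group did not agree on the pathway from intervention to pneumonia. On power, "the downside to conditioning on intervention could be reducing study power by reducing residual exposure variability". Finally, "intervention status will not be included for either pre or post-natal exposure as it will be superceded by measured exposure level".

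The section presents its minimal adjustment set as derived from the DAG. The a priori confounders in section 6.1 do not include arm. They are crowding, IRC, SES (which may incorporate nutrition data), sex, birthweight or its z-score, age, season, vaccination status, breastfeeding and a pandemic indicator. Section 5.2 also promises sensitivity analyses with other covariate sets, without naming any. Table 5 lists no subgroup by arm.

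**The concern.** On the section's own assumptions, arm is a cause of exposure and, by routes that bypass exposure, a cause of recorded pneumonia. That makes it a common cause, and a set that omits it leaves a back-door path open. Measured exposure can stand in for arm only if arm acts on recorded pneumonia solely through exposure and if the exposure error does not depend on arm. The section's working assumptions go against both conditions.

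What is at stake is interpretation. Part of the exposure slope comes from the contrast between arms. That part cannot be separated from effects of free fuel on household economy and behaviour, or from a difference in case detection. The bias could go either way: a direct benefit of the intervention would exaggerate a harmful slope, while better detection in the LPG arm would hide one. Section 5.2 sets out to identify a causal effect, so the reader needs to see how far the slope depends on the arm contrast.

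**Working it through.** **1. The plan's own figures.** 2984 infants × 4 quarters = 11,936, against about 12,000 stated in section 6.1. 175 / 2984 = 5.9%, against 6% stated in section 5.1. Both reproduce. The point disputes no stated figure.

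**2. Which paths are blocked.** The section 5.2 assumptions are set against the section 6.1 covariates.

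- Arm to breastfeeding: adjusted for.
- Arm to nutrition: partly, if the SES score incorporates nutrition data.
- Arm to vaccination: infant vaccination status is adjusted for; maternal vaccination is not listed.
- Arm to care seeking and screening: no term.
- Arm directly to pneumonia: no term.

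**3. Illustrative size.** The SAP gives neither the arm shift in exposure nor any direct arm effect, so both are assumed. Take one exposure X with within-arm SD 1, arms 1:1, mean lower by d in the LPG arm, no true smoke effect, and a direct arm risk ratio RR.

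- Var(X) = 1 + d²/4 and Cov(arm, X) = −d/4.
- Spurious log slope = log(RR) × (−d/4) / (1 + d²/4).
- Approximate SE of the unadjusted slope with 175 events = 1 / √(175 × Var(X)).
- SE inflation from adding arm = 1 / √(1 − R²), with R² = (d²/4) / (1 + d²/4).

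With RR = 0.8, log(RR) = −0.223:

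- d = 0.75: slope 0.223 × 0.1875 / 1.1406 = 0.037, so risk ratio 1.04. SE 0.071. R² 0.12, inflation 1.07.
- d = 1.0: slope 0.223 × 0.25 / 1.25 = 0.045, so 1.05. SE 0.068. R² 0.20, inflation 1.12.
- d = 1.5: slope 0.223 × 0.375 / 1.5625 = 0.054, so 1.06 (1.055 before rounding). SE 0.060. R² 0.36, inflation 1.25.

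The bias is about 0.5, 0.7 and 0.9 of a standard error. Over the same shifts, RR = 0.9 gives about 1.02 to 1.03 and RR = 0.7 about 1.06 to 1.09. RR = 1.25 reverses the sign, giving about 0.96 to 0.95.

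**4. Simulation check.** 400 logistic fits were run per scenario, with 2984 infants, 4 quarters and about 175 events. Results are per total exposure SD.

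- RR = 0.8, arm omitted: odds ratio 1.05 at d = 1 and 1.06 at d = 1.5, rejecting the null in 9% and 12% of runs.
- RR = 0.8, arm included: odds ratio 1.00 and 0.99, rejecting in 4% of runs.
- No direct arm effect, arm omitted: rejection about 6% at both shifts, which shows the simulation noise around the nominal 5%.

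**5. What arm adjustment does to attenuation.** Assume classical error with within-arm reliability r and no direct arm effect.

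- The adjusted slope is multiplied by r.
- The unadjusted slope is multiplied by (r + d²/4) / (1 + d²/4).
- r = 0.5: at d = 1, 0.5 / 0.60 = 0.83, so the adjusted slope is 17% smaller; at d = 1.5, 0.5 / 0.68 = 0.74, 26% smaller.
- r = 0.3: at d = 1, 0.3 / 0.44 = 0.68, 32% smaller; at d = 1.5, 0.3 / 0.552 = 0.54, 46% smaller.

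The two estimates can therefore differ considerably with no confounding by arm at all.

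**The case against.** The omission is deliberate and disclosed, and the power argument is real. At a direct RR of 0.9, the squared bias (0.0003 to 0.0006) is smaller than the variance that adjustment adds (0.0007 to 0.0021), so leaving arm out gives the lower mean squared error. At 0.8 this reverses. The arm effects are worded as possibilities and working assumptions, one of them disputed within the group. Some paths are already partly blocked. Section 5.4 will report completeness of ascertainment and will consider weighting or imputation if at least 10% of screenings are incomplete, though neither is stated by arm. The calculation uses one exposure. Section 6.1 fits prenatal and postnatal terms together and includes the baseline reading in the prenatal mean, which would divide the bias and dilute the prenatal contrast.

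All of this stands. It supports keeping the unadjusted model as primary and limits what can be said about size. It does not rescue the claim that the set follows from the DAG or that exposure makes arm redundant, and lack of consensus is itself a reason to show both estimates.

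A reader might also infer that the SAP forbids arm in every model. The text does not clearly say so. The exclusion sentence refers back to one limited to the primary analysis, and the general sensitivity commitment follows. An arm-adjusted model is unnamed, not plainly barred.

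**Conclusion.** The point holds as an internal inconsistency with a practical gap. Under the assumptions written in section 5.2, the set without arm does not identify the exposure effect, the stated reason that exposure replaces arm does not fit those assumptions, and no named analysis shows the consequence. This rests on the section's text, since the DAG figure is not available here.

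The minimal adjustment set also has an entry that runs the word intervention together with IRC, possibly through a lost comma. If arm was meant, the section contradicts itself outright.

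The size is illustrative: a spurious risk ratio of about 1.04 to 1.06 per within-arm SD for an assumed direct arm RR of 0.8 and shifts of 0.75 to 1.5 SD, below one standard error. Two stronger readings are tempting. One is that the primary slope is known to be materially biased; the document gives neither the arm shift nor the direct effect, so it supports no such statement. The other is that a causal reading should require the adjusted and unadjusted slopes to agree. Exposure rests on a few 24-hour readings, and error in these would shrink the adjusted slope by about 17% to 46% under the assumed reliabilities even without a direct arm effect, so disagreement would not show confounding.

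**What to change.** - Keep the unadjusted model as primary if wished.
- Name in section 6.1, as a sensitivity analysis for the primary endpoint, the same model with an arm indicator and, optionally, within-arm slopes. Report it beside the primary estimate.
- Report the comparison descriptively, with no agreement criterion. Note that adding arm widens the SE (about 7% to 25% for the shifts above) and increases attenuation from exposure error.
- Replace the sentence saying that measured exposure supersedes arm with the assumption actually made: no direct arm effect on pneumonia or its detection, and no arm-dependent exposure error.
- Clarify the entry joining intervention and IRC.

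The cost is one extra model per pollutant and a few lines of text. Because the ITT result is already reported (section 2.3) and the event counts are known (section 5.1), an arm-adjusted model added later would look post hoc.

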### **5.3. Baseline Participant Characteristics**

Baseline characteristics will be summarized, and completeness assessed as previously described.

### **5.4. Data Collection**

The exposure assessment methods have been described previously in detail. As noted above, we measured direct personal exposures in pregnant women once at baseline and twice during the trial period and measured indirect personal exposures in infants three times, at 3, 6 and 12 months. Results of this exposure assessment and the effects of the intervention have been reported separately. HAP exposure will be summarized in terms of timing and concentration, separately by each IRC according to subgroups defined in Table 5.

The person-time intervals per child can be considered as one continuous period, multiple weekly periods, or intermittent with interruptions for migration and recent cases. We will include the same respiratory outcomes reported in an intention-to-treat analysis and described in more detail in the published SAP and supplemental material for the severe pneumonia intention-to-treat analysis. Here we only briefly describe each respiratory endpoint, including data collection and processing.

The pneumonia case definitions are in Table 2. The primary endpoint of the trial included three criteria: 1) respiratory signs (cough or difficulty breathing), 2) evidence of severity (hypoxemia or danger signs), and 3) an objective diagnosis (hypoxemia, imaging, verbal autopsy, or advanced respiratory care).

Lung ultrasound was the primary imaging modality obtained and where logistical or regulatory barriers existed we obtained a chest x-ray. We defined tachypnea based on current World Health Organization thresholds ( $\geq 60$  breaths/minute for age 0-2 months and  $\geq 50$  breaths/minute for age 3-11 months). We will determine hypoxemia based on the physiologic threshold of  $\leq 92\%$  for altitudes  $<2,500$  meters above sea level and  $\leq 86\%$  for altitudes  $\geq 2,500$  meters above sea level. Children are also considered hypoxic, regardless of oxygen saturation, and assumed to have cough and/or difficult breathing if they are receiving advanced respiratory support at the time of evaluation, which includes any of the following: intubation and mechanical ventilation, non-invasive ventilation with continuous positive airway pressure support (CPAP), non-invasive ventilation with bi-level positive airway pressure support (BIPAP), or high-flow nasal cannula oxygen.

Children who died but were determined to have had pneumonia or symptoms and/or signs of a respiratory illness consistent with pneumonia by verbal autopsy were also considered a case of severe pneumonia. Adjudication panels determined the final interpretation of lung ultrasounds, chest radiographs, and verbal autopsies.

Screenings that are not complete enough for case ascertainment will be considered missing outcome data. If a substantial proportion of screenings ( $\geq 10\%$ ) are incomplete, we will consider imputation or weighting to reduce potential for bias.

The variables described in Table 3 were used to classify cases according to the two case definitions. Pneumonia endpoint variables were constructed (calculated) from individual data collection items across multiple data sources. Since these data processes are highly intricate, a panel of three data coders replicated the creation of the analysis dataset. This work was performed by the HAPIN Pneumonia Working Group members in collaboration with DMC. The final code for calculation of pneumonia outcome variables was provided by the HAPIN Pneumonia Working Group (PWG) and is available through the DMC.

**Table 3. Severe pneumonia case characteristics to be reported**

Variables	Type	Definition/Assessment Methods
Clinical signs		
Temperature $>38^{\circ}\text{C}$ , n (%)	Binary	
Average Heart rate	Continuous	Average of measurements when multiple measurements available Beats per minute
Average Respiratory rate	Continuous	Average of measurements when multiple measurements available Breaths per minute
Average SpO 2	Continuous	Average of measurements when multiple measurements available
Hypoxemia, n (%)	Binary	Categorized as SpO 2 $<93\%$ for Guatemala, India, and/or Rwanda. $<87\%$ for Peru. Yes/No
Wheeze +/- crackles, n (%)	Binary	Yes/No
At least one respiratory danger sign, n (%)	Binary	Any of the following: chest indrawing, severe chest indrawing, head nodding, persistent nasal flaring, grunting, stridor when calm, audible wheeze, tracheal tugging, intercostal recessions Yes/No
Chest indrawing, n (%)	Binary	Yes/No
Head nodding, n (%)	Binary	Yes/No
Persistent nasal flaring, n (%)	Binary	Yes/No

Grunting, n (%)	Binary	Yes/No
Stridor when calm, n (%)	Binary	Yes/No
Audible wheeze, n (%)	Binary	Yes/No
Tracheal tugging, n (%)	Binary	Yes/No
Intercostal retractions, n (%)	Binary	Yes/No
At least one general danger sign, n (%)	Binary	Any of the following: unable to drink or breastfeed, vomiting everything, convulsions, lethargy or unconscious, unable to feed, not moving at all or moves with stimulation only Yes/No
Unable to drink or breastfeed, n (%)	Binary	Yes/No
Vomiting everything, n (%)	Binary	Yes/No
Convulsions, n (%)	Binary	Yes/No
Lethargy or unconscious, n (%)	Binary	Yes/No
At least one neonatal danger sign, n (%)	Binary	Any of the following: unable to feed well, not moving at all or moves with stimulation only, grunting, severe chest wall indrawing Yes/No
Unable to feed well, n (%)	Binary	Applies to <2 months only. Yes/No
Not moving at all or moves only, n (%)	Binary	Applies to <2 months only. Yes/No
Grunting, n (%)	Binary	Applies to <2 months only. Yes/No
Severe chest indrawing, n (%)	Binary	Applies to <2 months only. Yes/No
Lung Imaging		
Lung ultrasound, n (%)	Binary	Primary endpoint pneumonia Yes/No
Chest radiography, n (%)	Binary	Primary endpoint pneumonia Yes/No
Clinical care		
Hospitalized, n (%)	Binary	Yes/No
Oxygen treatment, n (%)	Binary	Yes/No
Advanced respiratory supportive care, n (%)	Binary	Any of the following: High flow, NIV (CPAP/BiPAP), mechanical ventilation Yes/No
Outcome		
Mortality, n (%)	Binary	Death <30 days since diagnosis and/or Verbal Autopsy positive Yes/No

Children were permitted to meet the above case definition for severe pneumonia multiple times if the repeat event occurred either >14 days after the hospital discharge date or, if the hospital discharge data was not available or the child was not hospitalized, >30 days after the date the child met criteria for severe pneumonia. Implausible values and outliers identified from the variables that comprise the case definition will be considered missing. In addition to reporting the incidence rates of each endpoint, we will present the completeness of case ascertainment (e.g. proportion of reported healthcare visits with a screening, proportion of eligible cases with ultrasound assessment).

